5.2. Scientific Rationale

The study device was used in a pilot clinical trial (PPS-CTMD-15-001, ClinicalTrials.gov ID NCT02534493) that finished in October 2016 with promising results. Participants showed an average improvement in symptom severity scale (SSS) score of the Boston Carpal Tunnel Questionnaire (BCTQ) of 0.59 ± 0.68 points at 4 weeks (end of treatment period) compared to baseline SSS scores. After the 4-week treatment period, symptoms continued to improve for a total of 0.79 ± 0.74 points lower SSS compared to Baseline at 12 weeks.⁹ These results motivate the primary objective of this study.

The pilot study investigated the effects of the study device up to 4 weeks, but the trajectory of SSS did not indicate that improvement plateaued by 4 weeks. Thus, the treatment period is extended to 8 weeks in this study to determine if improvements continue with longer-term wear.

Analysis of the unilateral vs bilateral CTS patients showed a stark contrast in response. SSS of the unilateral patients improved 0.9 ± 0.5 points at 4 weeks and up to 1.2 ± 0.5 points at 12 weeks. In contrast, the bilateral patients appeared to show no improvement; however, the pilot study was not powered to detect differences in unilateral and bilateral subgroups. This difference is being explored as an exploratory objective in this study.

Most participants described the study device as being very comfortable and easy to wear. However, there were occasional comments about discomfort from the edges of the device. In Aim 1 of the NIBIB grant R44 EB024713-01, a series of experiments were conducted to investigate the applied pressures on wrists using tactile pressure sensors, the changes in median nerve dimensions using magnetic resonance imaging (MRI), and the changes in carpal tunnel or median nerve compression pressures in cadavers when the study device was applied to the wrist. This allowed the study device to be re-designed to fit a wider range of people and to reduce uncomfortable pressure points. A user feedback survey is incorporated in the present study to improve user satisfaction, which is critical for any practical application and success.

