7.2.3. Baseline Assessment

The Enrollment CRF captures Baseline assessment measures. These include:

- Date of birth/age
- Gender
- CTS severity (mild, moderate, or severe, from NCS)
- CTS diagnosis by hand (unilateral/bilateral, right/left/both)
- BCTQ and NPRS for affected hand(s)

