10.2. Sample Size Determination

A total of 102 subjects are required for this study, with 51 in each group.

The outcome measure used for calculations in the SSS of the BCTQ, which ranges from 1 to 5 with 1 being no symptoms (improved) and 5 being the worst symptoms (worsened).

A moderate effect size of 0.4 was chosen, assuming that study device efficacy is 0.4 greater than sham.

The pilot study experienced a drop-out rate of 20% (2 out of 13 total). With the longer treatment and follow-up times of this study, a higher drop-out is expected. Therefore the sample size calculation is modified by an estimated attrition rate of 25%.

The primary objective examines the 8 week vs baseline within-active group SSS change. Sample size determination explanation. The power analysis using the above results in a significance level of 0.05 and a power of 0.94*.

The secondary objective examines the change in SSS after 8 weeks between the active study device and sham groups. Sample size calculation is based on a parallel, one-sided t-test power analysis to identify an effect size of 0.4, standard deviation of 0.7 (based on the pilot study PPS-CTMD-15-001), significance level of 0.05, power of 0.8, and an estimated attrition rate of 25%.

The sample size was chosen to meet both the primary and secondary objectives.

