10.3. Randomization and Blinding Procedures

A simple randomization scheme is used to allocate subjects into the treatment group or the sham group. Site staff will be blinded to the randomization list and the Sponsor clinical research team blind to the allocation of each subject.

Blinding will be broken for each sham group participant at his/her first post-treatment follow-up (Week 12) so that the site can offer the sham group participant the opportunity to try the active study device. Complete blinding will be broken at the end of the study when all data has been entered and validated and the database has been locked.

Blinding may be broken if a subject experiences a SAE and if knowledge of the device is necessary for proper medical treatment of the SAE. Due to the low risk and minimal side effects associated with the device from previous studies, unblinding in most cases is not deemed necessary for medical treatment.

The subject's assigned site must obtain approval from the Sponsor to break the blind. After approval, the Shipping Associate responsible for randomization will provide the assignment for the subject in question. After a subject's treatment has been revealed, this must be noted along with reasons for breaking the blind in the subject's records and in the Deviation/Violation Log.

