10.5. Statistical Analyses

The primary efficacy endpoint is the improvement (reduction) in SSS of the treatment group at 8 weeks after the first day of device wear. The primary efficacy endpoint will be analyzed using a paired, one-sided t-test.

The secondary efficacy endpoint is the improvement (reduction) in SSS of the treatment group compared to the sham group at T4 (8 weeks after the first day of device wear). The secondary endpoint will be analyzed using a two sample one-sided t-test.

A repeated measures analysis of variance will be used to evaluate changes over time in both the active and sham groups.

The exploratory endpoints will be analyzed using descriptive methods.

Safety analyses will be performed on all subjects that received treatment.

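### The Week 8 active-versus-sham test makes no use of unilateral/bilateral status, a recorded baseline factor that the pilot tied to response; prespecifying it as a covariate is a cheap gain in efficiency of uncertain size

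*Combined protocol and SAP*

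**What the plan says.** - **Test.** Section 10.5, on active versus sham at 8 weeks: "The secondary endpoint will be analyzed using a two sample one-sided t-test". No covariate is named.
- **Allocation.** Section 10.3: "A simple randomization scheme is used to allocate subjects into the treatment group or the sham group". No stratification is described.
- **Baseline data.** Section 7.2.3 lists among the enrolment measures "CTS diagnosis by hand (unilateral/bilateral, right/left/both").
- **Pilot evidence.** Section 5.2: "Analysis of the unilateral vs bilateral CTS patients showed a stark contrast in response". It continues: "SSS of the unilateral patients improved 0.9 ± 0.5 points at 4 weeks and up to 1.2 ± 0.5 points at 12 weeks". Bilateral patients are described as apparently not improving, with no figure, and the section adds that the pilot lacked the power to compare the two subgroups. Over all pilot participants the improvement was 0.59 (SD 0.68) at 4 weeks and 0.79 (SD 0.74) at 12 weeks.
- **Sample size.** Section 10.2: "A total of 102 subjects are required for this study, with 51 in each group". For the between-group objective: "Sample size calculation is based on a parallel, one-sided t-test power analysis to identify an effect size of 0.4, standard deviation of 0.7", with "significance level of 0.05, power of 0.8, and an estimated attrition rate of 25" percent. The SD is attributed to the pilot.
- **Where laterality is used.** Section 4 makes it an exploratory subgroup question at 4 and 8 weeks, and 10.5 assigns exploratory endpoints to descriptive methods. Section 4 also lists an active-versus-sham comparison at Week 12, for which 10.5 names no specific test.

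**The concern.** The primary endpoint is a within-arm change, so the evidence that the device does better than sham comes from the secondary comparison, planned at a power of only 0.8. The protocol singles out one recorded baseline factor as strongly associated with SSS change, yet neither the allocation nor the between-group test uses it. Whatever variation laterality explains stays in the error term. If the two arms differ by chance in their share of unilateral patients, the planned analysis also has no prespecified way to account for it. Adding the covariate after seeing an imbalance would be post hoc.

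**Working it through.** **1. Reproduce the plan's figure.** Inputs from 10.2: difference 0.4, SD 0.7, one-sided 0.05, power 0.8, attrition 25%.

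n per arm = 2 × (1.645 + 0.842)² × 0.7² / 0.4² = 37.9, so 38. Inflated: 38 / 0.75 = 50.7, so 51 per arm and 102 in total. This agrees with the plan. Power of the t-test with 38 completers per arm (74 df) is 0.795.

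**2. What the pilot figures allow one to say about laterality.** Section 5.2 gives no bilateral mean, bilateral SD or subgroup sizes. *Assumptions:* bilateral mean change 0, and a common within-group SD of 0.5.

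- Implied unilateral share: 0.59 / 0.9 = 0.656 at 4 weeks; 0.79 / 1.2 = 0.658 at 12 weeks.
- At 4 weeks, between-group variance = 0.656 × 0.344 × 0.9² = 0.183. Adding 0.5² = 0.25 gives 0.433, an SD of 0.66 against the reported 0.68. Share explained = 0.183 / 0.433 = 42%.

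This depends on the undisclosed split. *Assumption:* 11 subjects analysed (the 13 in 10.2 less 2 drop-outs). The bilateral mean then follows from the overall mean, and the share is the between-group sum of squares over the total, 10 × 0.68² = 4.62:

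| Unilateral / bilateral | Implied bilateral mean | Between-group SS | Share explained |
|---|---|---|---|
| 6 / 5 | 0.22 | 1.27 | 27% |
| 7 / 4 | 0.05 | 1.85 | 40% |
| 8 / 3 | −0.24 | 2.82 | 61% |

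So roughly 40% is consistent with the text, within a range of about 27–61%. It describes device users at 4 weeks.

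**3. Effect on power.** Keep the total SD at 0.7 in each arm (variance 0.49), a unilateral share of 0.656 and a gap of 0.9 on active. A model with arm and laterality as main effects removes share × (1 − share) × (average of the two arms' gaps)². Power is then computed with 38 per arm and 73 df:

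| Gap on sham | Average gap | Variance removed | Residual SD | Power |
|---|---|---|---|---|
| 0.9 (shared) | 0.9 | 0.183 | 0.554 | 0.93 |
| 0.45 (half) | 0.675 | 0.103 | 0.622 | 0.87 |
| 0 (active only) | 0.45 | 0.046 | 0.667 | 0.83 |
| No gap in either arm | 0 | 0 | 0.700 | 0.79 |

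Simulation gives the same values to two decimals, and type I error with adjustment stays close to 0.05.

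**4. Chance imbalance.** With 38 per arm, the difference in unilateral share has SD √(2 × 0.656 × 0.344 / 38) = 0.109. A difference of at least 15 percentage points occurs in about 17% of trials. If the 0.9 gap is shared by both arms, that shifts the estimate by 0.9 × 0.15 = 0.135, a third of the planned 0.4. If the gap exists only on active and the imbalance is split evenly around the expected share, the shift is 0.9 × 0.075 = about 0.07.

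**The case against.** The case for leaving the test as it is has real substance.

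- **The planned test is valid.** Under simple randomisation, chance imbalance is already part of the sampling variance. The planning SD of 0.7 comes from a pilot in which both kinds of patient took part, so the standard error reflects laterality. This stands: there is no bias over repeated trials and no inflation of type I error.
- **The evidence is thin.** It comes from about a dozen device users. Section 5.2 itself cautions about power for this contrast and also reports a later redesign of the device, which weakens transfer. This stands too.
- **The exploratory question in Section 4 is about differing response to treatment.** On that reading the gap belongs to the active arm and the gain is only about 3 points. The documents report no sham data, so the larger gains cannot be assumed. A main-effect term would also not fully model such an interaction.
- **Any gain beyond adjustment for baseline SSS has not been computed.** Correct; the figures above compare against a wholly unadjusted test.
- **Laterality is not overlooked.** It is a named exploratory subgroup. True, but that does not bring it into the between-group test.

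A reader might infer that the pilot shows laterality to explain 42–56% of the variance. The documents do not support that. Both ends need an assumed bilateral mean of 0 and equal SDs. The upper end (0.658 × 0.342 × 1.2² = 0.324; 0.324 / 0.574 = 56%) uses pilot Week 12, eight weeks after that pilot's treatment ended.

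These points limit the size of the claim. They do not remove the case for prespecifying the covariate, because adjustment costs almost nothing if laterality turns out to be irrelevant.

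**Conclusion.** The point holds as one of efficiency and of protection against chance imbalance. The between-group test omits a recorded factor that the protocol itself associates with response. Under the plan's inputs, adjustment moves power from about 0.80 to between 0.83 and 0.93 if the pilot's 0.9-point gap is real, depending on how much of it also appears on sham, and leaves it unchanged if the pilot contrast is chance. These figures assume about 66% unilateral patients, a total SD of 0.7 in each arm, and that the 4-week gap carries over to 8 weeks.

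Two stronger readings should be resisted. The t-test is not invalid, and the sample size is not wrong. Nor is Week 8 the only randomised comparison of efficacy, since Section 4 also lists Week 12.

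**What to change.** In 10.5, analyse the Week 8 active-versus-sham comparison with a linear model of change in SSS on arm and prespecified unilateral/bilateral status, alongside any other baseline covariate that is prespecified. Test the arm term one-sided at 0.05. State that the same model applies to the Week 12 comparison in Section 4. Keep the unadjusted two-sample t-test as a supporting analysis. Leave the stated power at 0.8, since the gain depends on an unknown sham-arm gap.

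The cost is a sentence or two in the analysis section and one degree of freedom (73 instead of 74). The variable is already collected at enrolment. The downside is that there may be little gain, or none, if laterality proves unrelated to change on sham.

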2.1. Study Synopsis

Title	Randomized Controlled Clinical Trial of Non-invasive Device to Alleviate Symptoms of Carpal Tunnel Syndrome
Study Description	Sham-controlled, multi-center and remote patient-centered randomized controlled clinical trial to investigate the efficacy of a novel non-invasive, unobtrusive study device in reducing symptoms of carpal tunnel syndrome (CTS). Daily wear of the study device is expected to significantly reduce symptom severity (evaluated by the Boston Carpal Tunnel Questionnaire) in mild to severe CTS-diagnosed patients. Subjects are randomized into the active device group or sham group for 8 weeks, then followed for 12 weeks post-treatment.
Objectives	Primary: Investigate whether daily wear of the study device significantly reduces patient-reported CTS symptom severity. Secondary: Determine whether there is a difference between the active device group and sham group. Investigate whether changes in symptoms are sustained or continue post-treatment.
Endpoints	Primary: BCTQ-SSS of the treatment group at 8 weeks compared to Baseline. Secondary: BCTQ-SSS at 8 weeks and at post-treatment timepoints between the treatment and sham groups
Study Population	Sample size: 102 (51 in each arm) Adults diagnosed with mild to severe CTS, ages 21-65 of any gender Any geographic location within the United States
Phase	Confirmatory/pivotal
Sites	At least 3 physical sites located in the United States (national enrollment)
Study Device	Stiffness-optimized thermoplastic curved band that has a strong biocompatible adhesive in the center of the concave side of the device. Device is designed to decompress the median nerve and thus relieve symptoms of carpal tunnel syndrome.
Study Duration	Approximately 12 months
Participant Duration	5 months

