3.3.2. Known Potential Benefits

Prolonged wear (anywhere from 1 week to 4 weeks) of the study device may reduce symptoms of CTS.⁹

The sham device may cause a placebo effect and reduce symptoms of CTS as well.

4. Objectives & Endpoints

Objective	Endpoints	Explanation
Primary		
Investigate whether daily wear of the study device significantly reduces patient-reported CTS symptom severity.	Symptom Severity Score (SSS) of the Boston Carpal Tunnel Questionnaire (BCTQ) in the treatment group at 8 weeks compared to Baseline.	The SSS is a validated combined measure of the patient's perception of the level and frequency of pain, numbness, tingling caused by CTS. 8 weeks is the end of the treatment period.
Secondary		
Determine whether there is a difference between the active device group and sham group.	Comparing SSS at 8 weeks and between the active device group and sham group.	Between group comparison conducted for the primary outcome variable at the primary endpoint (8 weeks).

Additionally, we will determine if this difference continues post-treatment.	Comparing SSS 1 month post-treatment (12 weeks) between the active device group and sham group.	Single timepoint at 12 weeks compared between groups for post-treatment analysis.
Exploratory		
Does CTS symptom improvement occur before 8 weeks?	Significant reduction in SSS compared to Baseline at any time point before 8 weeks.	Identification of significant SSS reduction before 8 weeks suggests a shorter minimum duration of wear.
Do unilateral and bilateral CTS patients respond differently to treatment?	Change in SSS at 4 and 8 weeks in a unilateral subgroup compared to a bilateral subgroup.	Unilateral patients showed significant SSS improvement in the pilot study, whereas bilateral patients seemed to show none. ⁹ Both 4- and 8-week timepoints compared in case a difference is seen before the end of treatment.
Do patients respond differently based on Baseline severity?	Change in SSS at 4 and 8 weeks in mild, moderate, and severe subgroups.	AANEM guidelines categorize CTS into 3 severity groups.
Describe the effect of study device treatment on patients with hormonal-induced CTS, such as pregnancy.	Change in SSS at or within 8 weeks in a subgroup of pregnant women.	The study device is hypothesized to work primarily for repetitive stress induced CTS. Pregnant women often develop CTS due to swelling of the tissue.

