5.1. Overall Design

It is hypothesized that daily wear of the study device will result in significant improvements in patient-reported symptom severity. It is also hypothesized that the effects from active study device treatment will be significantly greater than effects from sham treatment. In both cases, it is hypothesized that improvements will be sustained post-treatment.

This study is designed as a randomized, double-blind, sham-controlled, two-arm trial consisting of an eight-week treatment period (active study device or sham), followed by one required follow-up four weeks later (at week 12). After the required follow-up evaluation, the active device group can optionally continue to report symptom changes for an additional 8 weeks. The sham group participants can elect to wear the active study device for 8 weeks after completing their week 12 follow-up evaluation of the sham device. For both groups, completion through the optional follow-ups results in a 5-month patient duration.

There are two study groups: the active device group receiving the active study device and the sham group receiving a non-active sham device. Subjects will be informed that they have a 50:50 chance of receiving treatment or a sham. They will also be informed that if they receive sham device, they will be offered the active device 4 weeks into the post-treatment period. However, all subjects will not know what treatment they are on until the conclusion of the trial. Study devices are shipped directly to enrolled subjects from the Sponsor's designated shipping associate, which blinds site staff to group assignment.

There are (at minimum) three physical research sites but subjects are primarily enrolled remotely. The physical research sites are clinics that local subjects can physically go to if needed (e.g., medical concern, AE). Enrolled subjects are assigned to the PI of the geographically closest physical site.

Subjects are enrolled following confirmation of CTS in one or both wrists via a recent Nerve Conduction Study (NCS) and are asked to wear the assigned device daily for 8 weeks. The NCS is an electrodiagnostic technique used to confirm clinical diagnosis of CTS, with a 56% to 85% sensitivity and at least 95% specificity for CTS.¹⁵ The primary outcome measure, Symptom Severity Score (SSS) of the Boston Carpal Tunnel Questionnaire (BCTQ), is evaluated at:

- Baseline
- Once every 2 weeks during the 8-week treatment period

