- 4 weeks after the end of treatment (at week 12)

After week 12, the active device group can continue to complete follow-ups every 4 weeks for another 8 weeks. At the end of week 12, the sham group will be given the opportunity to wear the active study device for 8 weeks. These subjects will be evaluated once every 2 weeks during an 8-week treatment period with the active study device (similar to the initial treatment period).

For visual representation of the study design, see Section [2.2 Schedule of Events \(SOE\)](#).

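### The synopsis and the repeated-measures ANOVA do not confine the active-versus-sham comparison to Week 12, and the ANOVA has no stated rule for missed visits

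*Combined protocol and SAP*

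**What the plan says.** Section 10.5 names a paired one-sided t-test for the primary endpoint and a two-sample one-sided t-test for the between-group endpoint, both at 8 weeks. It then adds: "A repeated measures analysis of variance will be used to evaluate changes over time in both the active and sham groups". It gives no list of visits, no contrast and no handling of missed visits. It names no test for the Week 12 group comparison.

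The endpoint definitions differ. The synopsis (2.1) has "Secondary: BCTQ-SSS at 8 weeks and at post-treatment timepoints between the treatment and sham groups", and describes the follow-up as "Subjects are randomized into the active device group or sham group for 8 weeks, then followed for 12 weeks post-treatment", which runs to Week 20. The table in Section 4 restricts the comparison: "Single timepoint at 12 weeks compared between groups for post-treatment analysis".

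On what happens after Week 12, Section 5.1 says "The sham group participants can elect to wear the active study device for 8 weeks after completing their week 12 follow-up evaluation", and that "the active device group can optionally continue to report symptom changes for an additional 8 weeks". Section 7.5 exits a sham subject who declines the active device. Section 10.3 breaks the blind for each sham participant at Week 12 so that the offer can be made. Section 10.4 limits the analyses to subjects who completed the 8-week treatment period.

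**The concern.** By the day row of the schedule in Section 2.2, both arms have BCTQ assessments on Days 112 and 140 (Weeks 16 and 20). An analyst who follows the synopsis, or who takes the ANOVA sentence at face value, could include them. Those visits set active-arm subjects who have stopped wearing the device, and who chose to keep reporting, against unblinded former sham subjects now wearing the active device. The outcome is self-reported. Such a contrast is not the sham-controlled effect.

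The ANOVA is also the only method listed in Section 10.5 that could serve the Week 12 comparison or the hypothesis in Section 10.1.2 that changes are sustained after treatment stops. Its visit window and its handling of missed surveys therefore bear on a stated secondary objective. If they are left open, the window can be chosen after sham subjects have been unblinded.

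**Working it through.** **1. The plan's own figure.** Inputs from Section 10.2: difference 0.4, SD 0.7, one-sided 0.05, power 0.80, attrition 25%.

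- n per arm = 2 × (1.645 + 0.842)² × 0.7² / 0.4² = 37.9, rounded up to 38.
- 38 / 0.75 = 50.7, rounded up to 51 per arm, 102 in total.

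This matches the plan. The sample size rests on the Week 8 t-test. The 38 per arm is what remains after the 25% attrition has been taken out.

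**2. Who supplies SSS after Week 12.**

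| | Active arm | Sham arm |
|---|---|---|
| Device after Week 12 | None (7.4) | Active device, or exit if declined (7.5) |
| Reporting | Optional (5.1) | Only those who accept the active device |
| Blind | Not broken at Week 12 | Broken at Week 12 (10.3) |

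Crossover is elective, but decliners exit. As planned, every sham-arm score after Week 12 therefore comes from a subject who accepted the active device.

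**3. Effect of including Weeks 16 and 20 (illustration).** Assume a difference of 0.4 in favour of the active device at Weeks 2, 4, 6, 8 and 12, a difference d at Weeks 16 and 20, and equal weight for the seven visits. Average = (5 × 0.4 + 2 × d) / 7.

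| Assumed d | Average | Fall from 0.4 |
|---|---|---|
| +0.2 | 2.4 / 7 = 0.34 | 14% |
| 0 | 2.0 / 7 = 0.29 | 29% |
| -0.2 | 1.6 / 7 = 0.23 | 43% |

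The documents give no value for d.

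**4. Complete cases to Week 12 (illustration).** Take 38 per arm with a Week 8 score. Assume each of the other four follow-ups (Weeks 2, 4, 6 and 12) is missed independently with probability p. Number complete = 38 × (1 - p)⁴.

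| Assumed p | Fraction complete | Per arm |
|---|---|---|
| 2% | 0.92 | 35 |
| 5% | 0.81 | 31 |
| 10% | 0.66 | 25 |

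The documents give no missed-visit rate. Gaps are possible among retained subjects, because Section 7.7 leaves withdrawal for missed follow-ups to the sponsor's judgement and Section 10.4 requires completed treatment, not every survey.

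**The case against.** Much of the protocol already treats Week 12 as the boundary. Section 4 fixes the post-treatment comparison there. Section 5.1 ends its list of SSS evaluations there and calls it the one required follow-up. The schedule does not mark the Week 16 and 20 assessments as required, and Section 6.6 treats the main part of the trial as over after Week 12. This stands: the fault is a synopsis that disagrees with Section 4 and an analysis section that does not settle the matter, not a plan with no cut-off anywhere.

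A reader might infer that the ANOVA drops everyone with a missed visit. No section says so. Complete-case use is the normal behaviour of the classical method. What the documents support is that the handling of missed visits is not stated.

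A reader might also take the 29% dilution as an expected result. Section 10.5 does not name a visit-averaged group difference as an estimate, and zero at Weeks 16 and 20 is only one of the assumed values. Nothing here shows that the effect would reverse: all three averages above stay positive.

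Nor should the 25% attrition be charged to the ANOVA. It is already allowed for in the 38 per arm, and the per-protocol rule removes those who do not complete treatment. Only intermittent misses remain. Counting Week 8 as a fifth visit at risk would give 0.95⁵ × 38 = 29 at p = 5%, but the calculation starts from subjects with a Week 8 score, so 31 is the consistent figure.

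**Conclusion.** The concern holds as an inconsistency and an under-specified analysis. As worded, the synopsis endpoint admits comparisons at Weeks 16 and 20 that are not active versus sham. The ANOVA sentence sets no window that would exclude them, and no test is named for the Week 12 comparison that Section 4 does specify.

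The size depends on assumptions outside the documents: a seven-visit average of 0.34 to 0.23 in place of 0.4 for d from +0.2 to -0.2, and 35 to 25 complete cases per arm out of 38 for missed-visit rates of 2% to 10%. The first range matters only if a visit-averaged difference is reported, and the second only if the ANOVA is run on complete cases.

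A reader might infer that the main result is compromised. It is not: the primary test, the Week 8 between-group test and the total of 102 do not use the ANOVA or any later visit.

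**What to change.** - **Synopsis (2.1):** change the secondary endpoint to SSS at 8 weeks and at 12 weeks between the groups, in line with Section 4.
- **Section 10.5:** replace the ANOVA sentence with a mixed model for repeated measures on Weeks 2, 4, 6, 8 and 12 only. Include arm, visit, arm-by-visit and baseline SSS, keep subjects with partial data, and report active-minus-sham contrasts at Weeks 8 and 12. This also supplies the missing method for the Week 12 comparison.
- **After Week 12:** report SSS descriptively by arm, labelled open-label, with no test between groups.
- **Section 10.4:** if the model is to include all randomised subjects with any follow-up SSS, amend the per-protocol population for this analysis as well. Otherwise the two sections will contradict each other.
- **Sections 5.1 and 7.4:** reconcile them. The first offers the active group optional follow-up to Week 20, while the second exits that group at the end of Week 12.

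The cost is a few wording changes and slightly more analysis work. No new data are needed and the sample size does not change.
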